## 5.0 Study Procedures

## 5.1 Study Design

Overview: 150 Veterans with a positive DVBIC screen for deployment-related mTBI sustained during the OEF/OIF/Persian Gulf eras confirmed by Parts A-C of the VA TBI Identification Clinical Interview (Vanderploeg et al, 2012), with reported loss of consciousness < 30 minutes or if they either meet diagnostic criteria for PTSD based on the Mini International Neuropsychiatric Interview (MINI) or have trauma- or combat-related stress (CS) of at least moderate severity, as defined by either a PTSD Checklist (PCL) score >34 (Kimerling, 2009) or Combat Exposure Scale (CES) score >23 (Keane et al., 1989), a consenting spouse/cohabiting partner and a Montreal Cognitive Assessment (MoCA) (Nasreddine, 2005) score ≥ 19 will be randomized to receive either: 1) six months (12 bi-monthly sessions) of MFG- mTBI-C, a psychoeducational rehabilitation and skills-building intervention after 2-3 individual couples "Joining" sessions; or 2) six months (12 bimonthly sessions) of Group Health Education (GHE), a structured didactic intervention delivering information and general recommendations to address health problems common in the OEF/OIF/Persian Gulft cohort. Participants will be assessed pre-treatment, immediately post-treatment, and 6 months post-treatment. A Diversity Committee will ensure representative ethnic/racial enrollment and cultural competence. The Diversity Committee will be chaired by [name] and will additionally comprise a member from each site with expertise in ethnicity/racial issues, including treatment, recruitment and retention in clinical research ([name], JJP VAMC and [name], VAMHCS). Prior to enrollment, the committee will help each site develop a diversity recruitment plan, individualized to the local catchment area, participating facilities and support groups. Weekly coordinator calls throughout the study will include a discussion of ethnic minority enrollment rates for each site. A committee member will attend a call monthly to review enrollment, retention and develop enhanced outreach strategies if goals are not being met. Data will be analyzed using an intent-to treat analysis with paired comparisons between treatment groups on primary (Veteran community integration) and secondary (Veteran interpersonal skills, marital adjustment, caregiver burden) outcome variables using mixed effects regression models. The study research tasks and our timeline to achieve them are presented in Table 4 below.

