Intervention Testing Procedures-Randomization and Maintaining Blind: Following informed consent enrollment, couples will be randomized to one of two treatment conditions (75 to each condition) within each VISN: 1) MFG-mTBI-C, or 2) GHE. To maximize adherence to intervention protocol and avoid inadvertent cross-contamination, each of the two educators at each site will conduct only one intervention, either MFG-mTBI-C or GHE. We will take precautions to ensure the RA's performing outcome assessments and other relevant persons are blind to study condition: 1. Subjects will be randomized to treatment condition using Proc Plan in SAS by an independent research staff member from another project who will place treatment assignments in separate envelopes according to the randomization sequence. To avoid recruitment and/or assessment bias, envelopes will be opened by the independent researcher after informed consent procedures in sequence, and assigned participants will be given a new # according to the randomization schedule; 2. The list linking participant code with treatment assignment will be maintained in a locked cabinet by the PI (who will not perform assessments) and by the study biostatistician (who is in a different location); 3. RA's performing assessments will be blind to educator assignment to treatment condition and will additionally be unaware that each educator is delivering only one treatment. 4. To make # 3 plausible, all educators (and other research staff) will participate in the initial training for both treatments. 5. The PIs will convey new assignments to the appropriate educator who will initiate contact to schedule Joining sessions. 6. All educators will deliver both treatments in closed rooms; 7. The rooms will be equipped identically, with a digital tape recorder; 8. The number and length of sessions will be standardized across conditions; 9. Both MFG-mTBI-C and GHE sessions will be recorded for adherence monitoring so that all participants will have identical files; 10. All data pertaining to session material (e.g., treatment notes) will be stored by educators in a locked or password-protected file separate from that used for assessment data; RA's will not have access to the session files. 11. Participants will be trained not to discuss study procedures except with their study educator or the PI, and study staff (educators and RA's) will only discuss study procedures and assignments with the PI or during supervision. 12. Veterans' VA clinicians will be blind to their treatment assignment; 13. Prior to data analysis, the biostatistician will add an electronic field for treatment group to the data base and the data analyst will be trained not to link assignment with ID code. Thus although RA's will be able to link participant names with ID codes needed for labeling and entering data, etc., they will be blind to treatment assignment using the above measures.

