### Tests of Specific Study Hypotheses:

### **Primary Hypotheses:**

Hypothesis 1: Veterans with mTBI treated with 6 months of multi-family group for couples (MFG-mTBI-C) will show improved community integration (primary outcome), and improved anger management and use of social support (secondary outcomes) compared with those treated in a health education group without training in communication skills or compensatory strategies; Changes in the primary study outcomes (Sydney Psychosocial Reintegration Scale) from baseline for each treatment group at each time point will be examined using paired t-tests or Wilcoxon signed-rank tests as appropriate. Differences in changes in mean Sydney scores from baseline between two treatment groups will be compared using t-tests or Wilcoxon rank-sum tests as appropriate at each time point. Linear mixed models will be used to examine changes in scales over time and to examine whether the effects of MFG-mTBI-C on the Sydney and secondary Veteran outcomes (DERS and social support scales) vary with time and study sites adjusted for the time-dependent treatment, imbalanced baseline prognostic factors (if applicable), and control variables relating to combat/ injury exposure (mechanism of injury (blast vs. other), # deployments, # TBI's and degree of exposure to war zone violence/threats). In addition, Spearman correlation coefficients will be used to assess associations of changes in the Sydney with changes in Veteran symptoms from baseline at each time point and to examine whether degree of associations increases over time among Veterans treated with MFG-mTBI-C. If significant patterns over time are observed in any of these variables, mixed models will then be used to examine the effects of the variables identified on CI change over 6 months post treatment.

Hypothesis 2: Caregivers whose Veteran spouse/partners are treated with MFG-mTBI-C will show reduced burden (primary caregiver outcome) over the course of treatment and in the 6-month follow-up period relative to caregivers whose Veteran partners are treated in a health education group. The analytic plan proposed in Hypothesis 1 will be used for assessing effects of MFG-mTBI-C on changes in the CBI.

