## **Exploratory Hypotheses:**

Using the same analytic approach outlined for Hypothesis 1, we will explore the hypotheses that Veterans with mTBI treated with 6 months of multi-family group for couples (MFG-mTBI-C) will show improvement in PTSD and depressive symptoms relative to Veterans treated with group health education (GHE) with their partners, in separate analyses. Power calculation: Our power calculations are based on pilot data from our open trial of MFG-mTBI for the primary study outcome, Veteran community integration, assessed by the Sydney Psychosocial Occupational Activity scale, and for the primary spousal outcome: caregiver burden. As we have no control group to allow us to calculate an effect size for differences in pre-post-treatment change between treatment groups, we have based our calculations on available data and calculated a range of scenarios. Our calculations assume the same mean pre-post-treatment changes on the Sydney (3.9) and Caregiver Burden Inventory (CBI) (18.0), as observed in the pilot study, and further assume that the standard deviation for the change in the control group is identical to that observed in the treatment group. The effect size is defined as (mt-mc)/mc, here mt and mc are the mean changes in the treatment and control groups respectively. The correlation between the baseline score and the follow-up score (rho) is also a factor impacting the standard deviation of the mean change, which in turn impacts the effect size associated with treatment group assignment. From the pilot study, these correlation coefficients are 0.83 and 0.84 for the Sydney and CBI. Using these data we are able to calculate power for a range of clinically significant (i.e., medium to large) effect sizes. Tables 8

and **9** below present the power calculations for each of the two outcomes based on the above assumptions for a two- sided, two-sample

Table 8: Power estimate-Veteran occupational activity

Table 9: Power estimate-Caregiver burden inventory

Effect	Attrition	N per cell	α	1-β
Liiot	7	it per cen	а	, b
Size		pre/post		
		attrition		
	. = 2.			
.5	15%	90/76	0.05	.87
.5	20%	90/72	0.05	.85
.5	2070	90/12	0.03	.00
.5	25%	90/67	0.05	.83
.6	15%	90/76	0.05	.94
	222/	00/70	0.05	
.6	20%	90/72	0.05	.92
.6	25%	90/67	0.05	.91
.0	2070	30/01	0.00	.91
.7	15%	90/76	0.05	.97
.7	20%	90/72	0.05	.96
	050/	00/07	0.05	0.5
.7	25%	90/67	0.05	.95

Effect Size	Attrition	N per cell pre/post attrition	α	1-β
.5	15%	90/76	0.05	.84
.5	20%	90/72	0.05	.81

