.5	25%	90/67	0.05	.79
.6	15%	90/76	0.05	.91
.6	20%	90/72	0.05	.89
.6	25%	90/67	0.05	.87
.7	15%	90/76	0.05	.95
.7	20%	90/72	0.05	.94
.7	25%	90/67	0.05	.93

Calculated for rho = .5; Pilot rho = .833Calculated for rho = .5; Pilot rho = .839

t-test, with alpha=0.05, rho=.50 and effect sizes ranging from .5 to .7. Although attrition in the pilot study was relatively low: 10%, we have conservatively calculated power for higher rates of attrition that that observed in our pilot work: 15%, 20% and 25%, at effect sizes lower than the 1.03 effect size observed for both measures. For the Sydney, we have good power to detect an effect of .5 for Occupational activity, assuming a correlation coefficient of .5, lower than the correlation observed in the pilot study of .83 even with 2.5 times the attrition observed in the pilot study. For the CBI we have good power to detect an effect of .5, lower than the correlation observed in the pilot study of .84, even at 20% attrition, and more power at higher effect sizes or lower levels of attrition. In the unlikely scenario that a substantially lower correlation is observed (.3) along with an effect size half that observed, our power falls somewhat short of conventional standards at higher levels (25%) of attrition (i.e., .70 for Sydney and .68, with a higher correlation coefficient, lower attrition or a larger effect size we have good power to detect a medium to large effect size.

We note that a larger sample size and repeated measures at follow-up will tend to increase the correlation coefficients and reduce the variance of the change over time, most likely resulting in an increase in power. The above power calculation is based on a two-sample t-test which is the simplest form of LMM (with random intercept only) and GEE. If the imbalance between groups on key participant characteristics is minimal, as we anticipate in this randomized trial, this calculation is justified. We chose the more robust approach of using the simpler model and powering our study for a worst case scenario (compared to the effect sizes and correlations

observed in our pilot data) to cover the possibility of a more substantial imbalance, rather than basing our calculations on a more sophisticated model involving many assumptions.

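### The ancillary symptom–Sydney correlation step looks for a rise over time in the MFG-mTBI-C arm only, where a rise can occur without any treatment effect

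*Combined protocol and SAP*

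**What the plan says.** Hypothesis 1 (section 5.6, Primary Hypotheses) is comparative: MFG-mTBI-C Veterans are expected to improve "compared with those treated in a health education group without training in communication skills or compensatory strategies". It is tested by between-group comparisons of Sydney change and by linear mixed models.

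A further step follows, introduced as an addition: Spearman coefficients relate Sydney change to symptom change at both follow-up visits. A second clause then narrows the question to one arm, its aim being "to examine whether degree of associations increases over time among Veterans treated with MFG-mTBI-C". The result has a use: "If significant patterns over time are observed in any of these variables, mixed models will then be used" to study how the flagged variables affect change in community integration after treatment.

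On the design, "Participants will be assessed pre-treatment, immediately post-treatment, and 6 months post-treatment". There are therefore two change scores per Veteran, and both are measured from the same baseline. Table 5 schedules the Veteran symptom measures with no distinction by arm.

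The plan does not say which symptoms are meant, what test or alpha defines a significant pattern, or whether the follow-on model includes treatment. The Bonferroni rule under General Approach covers models of treatment assignment on constructs with several measures. It does not mention this step.

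**The concern.** The question posed is whether, within one arm, the correlation between two changes is larger at 6 months than at post-treatment. A yes to that question does not show that MFG-mTBI-C alters the link between symptoms and community integration relative to GHE. The longer change score covers more time, so it can hold more true individual change relative to measurement error, and the correlation can then rise in any group of Veterans, treated or not.

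Two things are at stake. Ordinary co-variation of symptoms and functioning could be presented as a feature of the intervention. Symptoms could also be passed to the follow-on model for that reason, with no stated allowance for looking at several of them. The GHE data that would settle the matter are already being collected.

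**Working it through.** The plan gives no sample size, power or alpha for this step, so there is no figure to reproduce.

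**1. What an additive effect does.** If MFG-mTBI-C adds the same amount to every Veteran's change, all values in the arm shift together and their ranks stay the same. The Spearman correlation within the arm is therefore unchanged, and a rise in that arm carries no information about such an effect.

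**2. Why a rise can occur with no effect.** Inputs from the documents:
- The Treatment text in section 5.1 gives about 8 months of intervention in total, so the change scores span about 8 months and 8 + 6 = 14 months.
- On allocation, "couples will be randomized to one of two treatment conditions (75 to each condition) within each VISN". The power text's middle attrition rate of 20% leaves 75 × 0.80 = 60 per arm.
- On stability of the scores, "From the pilot study, these correlation coefficients are 0.83 and 0.84 for the Sydney and CBI".

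Assumptions not in the documents: each Veteran has a random intercept (variance 1) and, independent of it, a random slope (variance V per 6-month unit, correlated c between Sydney and symptom). Each visit has an error (variance E, correlated k between the two measures). Symptoms are scored so that improvement is positive. With t the interval in 6-month units:

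change–change correlation = (c·V·t² + k·2E) / (V·t² + 2E)

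Take V = .05, c = .6, E = .15, k = 0.
- Check against the pilot. The baseline variance is 1 + .15 = 1.15. At post-treatment t² = (8/6)² = 1.778, so the variance is 1 + .05 × 1.778 + .15 = 1.239. The baseline–post correlation is 1/√(1.15 × 1.239) = .84, close to the pilot's .83.
- Post-treatment: V·t² = .0889; correlation = .6 × .0889 / (.0889 + .30) = .14.
- 6 months: t² = (14/6)² = 5.444 and V·t² = .2722; correlation = .6 × .2722 / (.2722 + .30) = .29.

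The correlation doubles with no treatment effect in the model. With k = .3 it goes from (.0533 + .09)/.3889 = .37 to (.1633 + .09)/.5722 = .44, a smaller rise. With V = 0 it equals k at both visits, and there is no rise.

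**3. How often one arm would show it.** The two arms were simulated identically, with 60 per arm and visits at 0, 8 and 14 months. The increase was tested by a bootstrap z at two-sided 5% and counted when positive (2.5% expected if there is no true rise). This test is an assumption, since the plan names none.

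| Assumed structure | Rise detected, MFG-mTBI-C alone | MFG minus GHE difference significant |
|---|---|---|
| Drift, uncorrelated errors | 9–43% | 2–5% |
| Drift, error correlation .3 | 5–9% | 2–5% |
| No drift | about 2–3% | 2–5% |

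The ranges cover several parameter sets and repeat runs.

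**4. A second model.** Here the scores' autocorrelation decays between visits, with assumed reliability .9 and latent cross-correlation .6, and with 56 to 75 per arm. The one-arm rise was detected in 13–24% of trials with no effect when autocorrelation decayed, and in 2–3% when it did not. At 75 per arm, under one decay setting, the rate was 23.7% with no effect and 24.4% with an additive effect of .5 SD. The between-arm contrast was significant in about 3.5–5%.

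**The case against.** The strongest reply is that the step is secondary in every sense. It comes after the between-arm tests, its stated purpose is to assess associations, and no primary or secondary conclusion depends on it. Where the plan does claim mechanism or moderation (Hypotheses 3 and 4), it uses interactions with treatment group, and PTSD and depressive symptoms are compared with GHE under the exploratory hypotheses. All of this stands and limits the weight of the point.

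Several stronger readings are tempting, and the documents do not support them:
- *That the plan offers a rise as evidence of efficacy.* It nowhere says so.
- *That GHE is left out of the whole step.* The restriction to MFG-mTBI-C attaches to the clause about increase over time. The correlations at each time point carry no arm restriction, and the follow-on model names no arm.
- *That the rise will occur.* It can occur. Without drift or autocorrelation decay there is none, and a treatment effect that varies between Veterans could itself alter the correlations.
- *That 9–43% is a false-positive rate.* In those scenarios the correlation truly rises, in both arms. The figure is the chance of detecting that shared rise; the mistake would be to attribute it to treatment.

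What the reply leaves unanswered is that the plan does ask the increase question in one arm, uses significance to select variables, and states no contrast of these correlations with GHE.

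**Conclusion.** The point holds in a limited form. A rise in the symptom–Sydney correlation among MFG-mTBI-C Veterans cannot be attributed to MFG-mTBI-C, because the same rise can appear in GHE with no treatment effect. That conclusion needs only the one-arm restriction, the shared baseline and the unequal intervals, all of which follow from the plan.

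The size is uncertain. Detection of a shared rise ranged from about 2% to 43% per symptom at 60 per arm, depending on individual drift, slope correlation and error correlation, which the documents do not give. It also depends on the test assumed. Contrasting the arms kept the rate at 2–5% throughout. The between-arm tests of the Sydney and the Caregiver Burden Inventory are unaffected. This is worth correcting before unblinded analysis, but it is no threat to the main result.

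**What to change.** In section 5.6, Hypothesis 1:

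1. Compute the same Spearman coefficients in GHE, show both arms side by side at both visits, and label them descriptive.
2. Delete the one-arm significance gate to the follow-on mixed model.
3. If an MFG-specific link between symptoms and community integration is to be claimed, rest it only on the treatment-interaction terms of a mixed model for Sydney change fitted in both arms. Include symptom change, treatment, visit, symptom change × treatment, symptom change × visit, treatment × visit, and symptom change × treatment × visit. Name the symptoms in advance, for example PCL-M and CES-D-10, which match the PTSD and depression aim in section 3.0, and adjust for their number.

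The lower-order terms are needed. If symptom change × visit and treatment × visit are left out, the three-way term absorbs the rise common to both arms. In simulations with drift and no treatment effect it then rejected in 10–45% of trials, against 2–7% with both terms included.

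Hypothesis 2 and the exploratory PTSD and depression analyses borrow the Hypothesis 1 approach, so the amendment should say whether this step carries over to them.

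The cost is plan wording and a little code, with no new data. The interaction test is less powerful than the one-arm test, so fewer symptoms are likely to be declared significant.

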### **Secondary Hypotheses:**

Hypothesis 3: Improvement in community reintegration will be mediated by improvements in Couples Functioning and Veteran emotion regulation and interpersonal skills. An aim of this study is to develop a conceptual model of the therapeutic action of MFGmTBI-C. We will conduct exploratory analyses to evaluate the potential mediating role of hypothesized mediators, marital satisfaction/conflict assessed by the DAS, and Veteran emotion regulation and interpersonal skills, assessed by the DERS and Duke scales, following the approach described by Baron & Kenney (1986), which entails evaluating the bivariate associations in the model prior to multivariate modeling. If the bivariate associations between the predictor, outcome and potential mediating variable are all significant, a mediational hypothesis will be evaluated using hierarchical linear models or random effects models. For example, to evaluate the potential role of marital satisfaction in mediating improvement in community integration among couples treated with MFG-mTBI-C vs. GHE, we would enter treatment assignment and time effects in Step 1, followed by marital adjustment (DAS) efficacy in Step 2, and the interaction between marital adjustment and treatment group in Step 3. A significant main and group interaction effect for marital satisfaction would support a mediational hypothesis (Kraemer et al., 2002).

Hypothesis 4: Veterans with more intact baseline cognitive functioning will show greater improvement in community integration, emotion regulation and interpersonal skills and marital satisfaction. In order to evaluate the potential role of baseline neurocognitive status in moderating the effects of treatment, we will evaluate the interaction of baseline levels of impairment with treatment group in predicting treatment response, after controlling for imbalanced baseline prognostic factors. Preliminary analyses will be conducted to evaluate the bivariate associations between baseline neurocognitive test scores and change in primary and secondary outcomes over treatment, and multivariate—level analyses will be conduct only outcome variables with an association of at least .5 for 1+ of the neurocognitive measures, using mixed models to examine the moderating effect of neurocognition on CI and other secondary or intermediate outcomes.

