Table 4: Timeline of Research Tasks

Months	Research Task
0-5	Refine manual, develop adherence scale for control condition, Train educators
	and research assistants, IRB submission, approval
4-5	Specify procedures for random assignment; blinding assessors, develop
	databases, refine recruitment procedures with study and facility staff

5-38	Enroll and study 150 cases (75 treatment, 75 control); Follow-up assessments
39-44	Complete follow-up on last cohorts' cases for 6 months
44-48	Analyze, disseminate data

Tempo: In order to study 14 groups of 3-5 couples each (7 treatment, 7 control) per VISN (3 and 5), each VISN will begin recruitment and individual sessions for two groups, one treatment, one control in study month 5, and continue to enroll and initiate treatment for two additional groups, one in each study condition, every 4-5 months until all groups have been completed and followed, in study month 44. This design will in most cases avoid a long wait for participants between randomization and starting treatment. In cases where one treatment condition becomes "filled", in order to avoid long delays and possible attrition before starting treatment, and permit both interventions to be conducted in tandem, we will allow groups with as many as 8 and as few as 3 couples. The protocol also permits an additional "Joining" session to keep early enrolled couples engaged while later-enrolled couples are being assessed and 'joined". In terms of workload, although there will be overlap between groups, the more labor-intensive work of recruiting, consenting and meeting with individual couples will overlap with the less intensive bi-monthly group meetings for the previously-enrolled two groups and will therefore be feasible.

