missing data points and unequal intervals between testing occasions. Choices of variancecovariance structures to account for within-subject correlation will be made based on the AIC, BIC, or likelihood ratio statistic. All principal analyses will be conducted based on the intentionto-treat principle in which any participant randomized to a treatment arm remains in it regardless of adherence to or completion of treatment. We will measure the level of participation, and will conduct a sensitivity analysis that assesses the stability of the conclusions from this study with an intention-to-treat analysis versus an analysis that takes into account level of adherence. With multiple time points and variables representing outcomes at both the individual and couples level, the planned analyses involve multiple comparisons raise concerns about the increased likelihood that any single outcome will be found to be statistically significant based on chance alone. In order to minimize this risk, we have carefully selected a limited number of outcomes and clearly designated primary, secondary and exploratory outcomes. Our primary outcomes for the Veteran and for the caregiver are each represented by a single measure. For models evaluating the effect of treatment assignment on constructs represented by more than one measure, e.g., Veteran Emotion Regulation and Interpersonal Skills, we will employ Bonferroni's correction to adjust each observed p-value by the number of tests performed and have calculated power on this basis (see power calculations below).

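### Hypothesis 3 counts mediation as supported on a significant DAS-by-treatment interaction as well as a DAS main effect, so mediation with equal slopes in both arms would go unsupported about 95% of the time

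*Combined protocol and SAP*

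**What the plan says.** Section 5.6, Secondary Hypotheses, Hypothesis 3, proposes that improved couples functioning (DAS) and improved Veteran emotion regulation and interpersonal skills (DERS and Duke scales) mediate the gain in community integration. The plan gives the work exploratory status: "We will conduct exploratory analyses to evaluate the potential mediating role of hypothesized mediators".

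There are two stages. First comes a screen on pairwise associations: "If the bivariate associations between the predictor, outcome and potential mediating variable are all significant", the multivariate model is fitted. That model, illustrated with DAS, enters treatment and time in Step 1, "followed by marital adjustment (DAS) efficacy in Step 2, and the interaction between marital adjustment and treatment group in Step 3". The criterion for support follows: "A significant main and group interaction effect for marital satisfaction would support a mediational hypothesis".

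The section gives no other route to support. It does not say how to read a significant DAS effect in Step 2 with a null interaction in Step 3, it does not estimate or test the indirect effect, and it states no significance level for these tests.

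**The concern.** The Step 3 term asks whether DAS relates to community integration more steeply in one arm than in the other. That is a question about effect modification. In the same section, Hypothesis 4 uses an interaction with treatment for exactly that purpose, to test moderation by baseline cognition. Mediation is a chain: treatment moves the mediator, and the mediator moves the outcome once treatment is held fixed. The chain can be strong while the second link has the same slope in both arms.

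The plan's rationale does not predict unequal slopes. The model described with Figure 3 in section 5.1 has the intervention acting through couples coping. The literature cited there and in the Introduction for the second link concerns family functioning and outcome in general, not within a particular treatment. A Veteran who benefits from a better marriage in either arm fits that rationale, and the written criterion cannot pick up that pattern beyond chance.

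At stake is the answer to the mediation aim in section 3.0, which is also one of the three hypotheses in the abstract. A finding of no support would say very little about whether the mechanism operates.

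**Working it through.** **Plan's own figure.** The plan states no power or error rate for Hypothesis 3, so there is nothing to reproduce.

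**Inputs from the documents.**
- Criterion: DAS main effect and DAS-by-treatment interaction both significant (Hypothesis 3).
- Screen: treatment, DAS and outcome all pairwise associated (Hypothesis 3).
- Size: "Enroll and study 150 cases (75 treatment, 75 control); Follow-up assessments" (Table 4). Attrition of 15%, 20% and 25% (power section) leaves 75 x .85 = 64, 75 x .80 = 60 and 75 x .75 = 56 per arm.

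**Assumptions.**
- Alpha .05, two-sided, borrowed from the power calculation for the primary outcomes: "t-test, with alpha=0.05, rho=.50 and effect sizes ranging from .5 to .7".
- Path sizes in residual SD units, none of which the documents give: treatment to DAS (a) .5 to 1.0; DAS to community integration (b) .5 to .8; direct effect (c) 0 to .25.

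**Step 1: algebra.** Write DAS = a x T + error and Y = c x T + b x DAS + g x (T x DAS) + error. Mediation with equal slopes means a and b are non-zero and g = 0. Then

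P(criterion met) = P(main effect and interaction both significant) <= P(interaction significant) = alpha.

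So P(mediation not supported) >= 1 - alpha:

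| alpha | not supported, at least |
|---|---|
| .10 | 90% |
| .05 | 95% |
| .025 | 97.5% |
| .05/3 = .0167 | 98.3% |

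Neither n, a nor b appears in the bound, so a larger trial does not help.

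**Step 2: simulation check with equal slopes.** With least squares on a single follow-up (4,000 trials per setting; 56, 60, 64 and 75 per arm), the interaction was significant in 4.2% to 5.6% of trials. Main effect and interaction together were significant in 3.5% to 5.6%, depending partly on whether the main effect is read at Step 2 or Step 3. Adding the screen gave 0.9% to 5.6%. In a three-visit random-intercept mixed model (2,100 trials, 64 per arm, a = .8, b = .5, c = .2), the interaction was significant in 5.3% of trials and the DAS main effect in all of them.

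**Step 3: unequal slopes.** With a = .5, b = .5, c = .25, 60 per arm and 3,000 trials per setting, a slope difference of .3 met the criterion in about 35% of trials and a difference of .5 in about 75%. After the screen these fall to about 24% and 55%.

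**Step 4: what the fix delivers.** Equal slopes, 60 per arm, 3,000 trials per setting, 95% Monte Carlo interval for a x b:

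| a, b | c | written rule, with screen | interval, with screen | interval, no screen |
|---|---|---|---|---|
| .5, .5 | 0 | 1% | 22% | 79% |
| .5, .5 | .25 | 3% | 57% | 78% |
| .8, .6 | 0 | 3% | 61% | 99% |
| .8, .6 | .25 | 5% | 92% | 99% |

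Repeat runs varied by a few points, giving overall ranges of about 20-60% and 60-92% with the screen kept. The screen limits the gain because it also requires a significant treatment-outcome association. In the first row the standardized total effect is (a x b + c)/sqrt(1 + b^2) = .25/1.118 = .22, which 60 per arm rarely detects. In the last row it is .73/1.166 = .63.

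**The case against.** **The wording is permissive.** The sentence says what would support mediation, and the DAS model is introduced as an example. A reader might infer that the plan declares mediation absent when the interaction is null. It does not; the exact outcome is that mediation is not supported. But no other criterion is given, so the practical consequence stands.

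**Equal slopes are an assumption.** This is fair. Only the intervention arm trains partners to assist with rehabilitation, and section 5.1 says the control sessions leave couples' issues aside, so a steeper slope under treatment is possible. Step 3 shows the criterion then passes more often. The 95% belongs to the equal-slope case and should not be read as the failure rate under every form of mediation.

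**A positive result still means something.** A reader might infer that it would show only that slopes differ. Reaching Step 3 requires the pairwise associations to be significant, so a positive result also carries evidence on both links. What is missing is an estimate and interval for their product.

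**The criterion cites a methods paper.** That paper is not among the documents, so whether the sentence compresses it cannot be checked. The written conjunction is what an analyst would apply.

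**The analysis is exploratory.** Hypothesis 3 says so, and the covariates paragraph uses the same label. This limits the weight of the point but does not make the criterion correct.

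**Conclusion.** The criterion is wrong as written. With equal slopes and alpha .05, it leaves real mediation unsupported in at least about 95% of trials at any sample size. The bound rests on those two conditions alone. The alpha is borrowed from the primary power calculation. The Bonferroni sentence in General Approach, "we will employ Bonferroni's correction to adjust each observed p-value by the number of tests performed", concerns treatment-effect models and is not stated to cover Hypothesis 3; if it were applied to the three mediators, the bound would rise to 98.3%.

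The gain from correcting the rule depends on assumed path sizes and on the screen. A reader might infer a jump from 5% to 80% or 99%. Those higher figures hold only if the screen is dropped too. With it kept, the supportable contrast at 60 per arm is about 1-5% against 20-60% (a = .5, b = .5) or 60-92% (a = .8, b = .6).

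This should be fixed before analysis, but it ranks below defects in the primary analysis: the primary hypotheses, the sample size and the conduct of the trial do not depend on it.

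**What to change.** Replace the criterion sentence in Hypothesis 3 with wording to this effect: mediation is judged by the indirect effect, that is, the treatment effect on the mediator multiplied by the mediator's effect on community integration given treatment, with a 95% bootstrap or Monte Carlo confidence interval; it is supported if the interval excludes zero. The mediator-by-treatment term is kept where needed to allow arm-specific slopes, but its significance is not required.

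State that the same rule applies to the DERS and Duke mediators, and state the significance level and whether it is adjusted for three mediators. Whether to keep the bivariate screen is a separate decision, and the plan should make it explicitly because the screen sets most of the remaining loss.

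The cost is one paragraph of text and a few lines of code. No new data are needed. The change is best made before treatment assignment is added to the analysis database.
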